Sub Aim 2a) Compare the two interventions on rate of self-reported MRSA SSTI recurrence and repeat surgery over a 12 month follow-up period.

Sub Aim 2b) Compare the two interventions on patient-centered outcomes such as quality of life and school attendance as well as others informed by Aim 1 over a 12 months follow-up period.

Sub Aim 2c) Determine the burden and patient preferences regarding the decolonization protocol on families.

The proposed research will be conducted as a randomized controlled comparative effectiveness trial over three years. Aim 1 will be carried out over a six months period. For Aim 2, recruitment and randomization will be done over a period of approximately 12 months and will be followed by a 12 month long evaluation period. Interviews as well as recruitment and randomization will be carried out in the pediatric surgery outpatient clinic and over the phone for patients of the Emergency Department at Riley Hospital for Children in Indianapolis, IN. Evaluation will be done by trained research assistants through phone interviews (or data collection via US post and/or online via secure email link to REDCap) at approximately 6 weeks, 6 months, and 12 months.

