3.0 Inclusion/Exclusion Criteria

Eligible participants will be the following:

- Children/youth ages 3 months up to 18 years seen in the Riley Pediatric Surgery Outpatient Clinic for a follow up visit within a maximum of 90 days of the incision and drainage of a culture-confirmed MRSA abscess (regardless of where the abscess was drained)
- Children/youth ages 3 months up to 18 years who had an incision and drainage of a culture-confirmed MRSA abscess in the Riley Emergency Department or Riley Operating Room within a maximum of 90 days of enrollment (though target enrollment is the two weeks prior to enrollment)
- Household members of the patient who are between the ages 3 months up to 64 years

In order to enroll, the parent or legal guardian of the eligible patient must consent to the patient's as well as the parent's own participation and the patient, if age seven and older, must assent to participate.

The following children will be excluded due to the risk of a more complicated course:

- Children in need of additional abscess surgery at the time of follow up
- Children with documented immune deficiency
- Children who are previous burn victims and required specialized burn care
- Children with another medical condition may be excluded at the discretion of PI, e.g. for a condition that would be adversely affected by bleach baths.

The following children will also be excluded:

- Children <3 months of age
- Children with self/parent-reported history of sensitivity to chlorine bleach or mupirocin
- Children whose siblings/families have already been recruited into the study

The following family members will be excluded:

- Family members with a self/parent-reported history of sensitive to bleach or mupirocin or other condition that would preclude a bleach bath.
- Family members who cannot understand the verbal and written instructions.
- Families without a bathtub in their home and pregnant and nursing mothers will also be excluded.

For the Patient Advisory Board (PAB), the following inclusion criteria apply:

- Parents/legal guardians of children ages 3 months to 18 years who have undergone an incision and drainage procedure at Riley for an abscess (regardless of MRSA confirmation)
- Children and youth ages 9-18 who have undergone an incision and drainage procedure at Riley for an abscess.

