At the time of enrollment, those randomized to intervention 1 will receive written hygiene instructions and a form to document outcomes, such as missed school or work. Those randomized to (or placed in) intervention 2 will receive a "kit", which will include a bucket for measuring the water, two cups to be used for measuring bleach, Clorox bleach, mupirocin ointment, double sided q-tips for application of mupirocin, hygiene instructions, as well as a form to document outcomes. Participants will also receive a link to an online video demonstrating the accurate process for preparing the diluted bleach bath and administering the mupirocin. (www.youtube.com/watch?v=3RbtyLT071M&feature=youtu.be) For each intervention arm, the above materials will be sent via mail after enrollment or provided in person by a research assistant.

Outcomes Measures

The patient-centered outcomes we plan to measure are summarized below.

The results of PAB sessions performed during aim 1 of this study will further inform some of the patient-centered outcomes measures.

Recurrence of SSTI

 Percent of participants with recurrence of skin and soft tissue infection by parental report at 6 weeks, 6 months and 12 months.
Repeat surgery

 Percent of participants with repeat incision and drainage procedure by parental report at 6 weeks, 6 months and 12 months.
Adherence to intervention

 Participant adherence to intervention measured on a 5 point scale by parental report at 6 weeks Household adherence measured on a 5 point scale by parental report at 6 weeks Have you tried anything outside the protocol to reduce the risk of MRSA recurrence? If yes, then what? (6 weeks)
Side effects
Percent of participants with side effects from intervention by parental report at 6 weeks and 6 months.
Participant time committed to intervention
Estimated weekly time to adhere to intervention by parental report at 6 weeks
Quality of Life

 Participants' quality of life measured by parent-proxy report (or youth tool) of the PedsQL 4.0 (Pediatric Quality of Life Inventory) at recruitment, 6 weeks, 6 months, and 12 months. Impact on free time measured on a 5 point scale by participant (age\geq13) and parental report at 6 weeks
Impact on school attendance

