
 Participants' school attendance by parental report at 6 weeks, 6 months and 12 months
Impact on parents' work attendance

 Assessment of parents' work attendance by self report at 6 weeks, 6 months and 12 months
Other Patient Centered Outcomes

 Participant's level of pain and discomfort at incision site via NRS at enrollment and 6 weeks. Participant's level of knowledge on what MRSA is and how to prevent its recurrence at enrollment, 6 weeks, 6 months, and 12 months. Additional measures as suggested by Aim 1

Data Collection and Study Tools

In order to evaluate the outcomes identified above, data will be collected by RAs in person or by phone at enrollment, and through phone interviews at approximately 6 weeks, 6 months and 12 months as time allows within the study period. RAs will be trained to perform phone interviews to assess recurrence, adherence, side effects, quality of life and school/work attendance. When requested by the participant, data collection tools/questions may be mailed via US post and/or emailed via secure link to REDCap. For all practical outcomes, such as missed school and work, participants will have forms to help them document these outcomes to aid in recollection at follow up.

The data collection for specific outcomes is outlined below:

Recurrence of skin and soft tissue infection

An RA will contact a parent of participants by phone at approximately 6 weeks, 6 months and 12 months. Participants will be asked whether they have had a recurrence of MRSA SSTI since the previous contact. If the answer is yes, they will also be asked if and where medical care was sought, and if any interventions (surgery, antibiotics) were needed. In cases for which antibiotics were prescribed, the name of antibiotics and duration of course will be recorded.

Repeat surgery

In a continuation of the questioning as shown above, an RA will contact a parent of participants by phone at approximately 6 weeks, 6 months and 12 months. They will be asked whether participants needed another incision and drainage procedure for MRSA SSTI in the same or another body location. If the answer is yes, they will also be asked in what facility that was done and whether antibiotics was prescribed or not. In the cases for which antibiotics were prescribed, the name of antibiotics and duration of course will be recorded.

Adherence to intervention

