An RA will contact a parent of participants by phone at approximately 6 weeks after study randomization. The RA will ask parents of participants about adherence to interventions. The RA will initiate the conversations by saying “we are very interested to know what people think about the protocol”. For any of the interventions experienced (hygiene measures, mupirocin to nose, and bleach bath) participants will then be asked to report adherence. Adherence will be reported on a 5 point scale for child and other family members: We followed the instructions as recommended – always, sometimes, never.

For the purpose of analysis “always”, “never omitted more than one time/dose/bath in a row” and “never omitted more than one day/week in a row” will be considered adherent to treatment.

RAs will also ask: “Have you tried anything outside the protocol to reduce the risk of MRSA recurrence? If yes, then what?” This should capture any patients in the control arm who may be using decolonization regimens outside their designed protocol.

Side effects

An RA will contact a parent of participants by phone at approximately 6 weeks after randomization. The RA will ask parents of participants about side effects to interventions, for example: “Did any family member experience side-effects from the intervention? All parents will also be asked: “Dry skin and irritation in the nose or runny nose are sometimes reported in families, have any of your family members experienced those symptoms?”

Participant time committed to intervention

An RA will contact a parent of participants by phone at approximately 6 weeks after randomization. If participant report that they adhere to the protocol, the RA will ask parents to estimate the amount of time (in hours) per week they estimate the intervention took for all family members combined.

Quality of Life

Impact on quality of life will be measured by the use of Peds QL, Pediatric Quality of Life Inventory.²² The Peds QL was developed to measure health-related quality of life (HRQOL) in healthy children and adolescents and those with acute and chronic health conditions. The RA will administer the 23-item parent proxy report of the Pediatric Quality of Life Inventory in person or by phone at recruitment and at recruitment, and over the phone at approximately 6 weeks, 6 months, and 12 months. Participants 13 and older will be able to give self-report.

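### As written, both side-effect questions give a household answer and the symptom prompt merges skin with nose, although the outcome is a percent of participants at 6 weeks and 6 months

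*Combined protocol and SAP*

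**What the plan says.** All of this is in the combined protocol and SAP.

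- **Outcome.** The Outcomes Measures list in section 5.0 defines the side-effect outcome as "Percent of participants with side effects from intervention by parental report at 6 weeks and 6 months".
- **Questions.** The Side effects paragraph of section 5.0 describes a contact at about 6 weeks. It gives a general question, introduced as an example: "Did any family member experience side-effects from the intervention". It then gives a symptom prompt put to all parents: "Dry skin and irritation in the nose or runny nose are sometimes reported in families, have any of your family members experienced those symptoms". No other side-effect question names a symptom, and no follow-up is written for a yes.
- **Who may take part.** Section 3.0 lists among eligible participants "Household members of the patient who are between the ages 3 months up to 64 years". Section 5.0 directs the interventions to every household member who consents.
- **Finer capture elsewhere in section 5.0.** On adherence: "Adherence will be reported on a 5 point scale for child and other family members". On outside measures: "Have you tried anything outside the protocol to reduce the risk of MRSA recurrence? If yes, then what". On recurrence: "If the answer is yes, they will also be asked if and where medical care was sought".
- **Aim served.** Sub Aim 2c in section 2.0 is to "Determine the burden and patient preferences regarding the decolonization protocol on families".

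**The concern.** The outcome counts participants, but both written questions count families. A parent who answers yes has said that at least one person in the home had at least one of three complaints. The answer does not say whether the child was that person, or whether the complaint was on the skin or in the nose.

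Decolonization acts on both sites: bleach baths on the skin and mupirocin in the nose. A report built on these answers could give one overall figure per arm. It could not tell a family what the complaints were or whether the treated child had them. The outcome is also listed for 6 months, while the Side effects paragraph describes asking only at about 6 weeks.

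What is at stake is the descriptive account of side effects and its use for the burden aim. Recurrence and repeat surgery do not depend on these questions.

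**Working it through.** The plan states no side-effect rate and no test for this outcome, so there is no figure to reproduce. The main check compares question with outcome; the arithmetic only illustrates.

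**Unit.** If participants means index children, an any-member answer counts too many people. If it means all enrolled household members, one answer per family still cannot give a percent of people. Either way the written questions yield a percent of households. The general question has the same any-member wording, so it does not close the gap.

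**Who (illustration).** Assumed, not from the documents: dry skin s = 0.05, any nasal symptom b = 0.20, with symptoms and family members independent.

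- Chance that one person has any listed symptom: c = 1 − (1 − b)(1 − s) = 1 − 0.80 × 0.95 = 0.24.
- Chance that a household of m answers yes: 1 − (1 − c)^m.
- m = 2: 1 − 0.76² = 0.422. m = 4: 1 − 0.76⁴ = 0.666. m = 6: 1 − 0.76⁶ = 0.807.

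Independence is doubtful for runny nose and shared exposures. With positive clustering these figures are upper values; under complete clustering the household rate is 24%.

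Over a wider assumed range, person-level risk p from 0.02 to 0.20 and m from 2 to 5, still with independent members:

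- The household yes rate, 1 − (1 − p)^m, runs from 0.04 to 0.67.
- The chance that a yes includes the index child, p / [1 − (1 − p)^m], runs from 0.21 to 0.56.

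**Which (illustration).** Take one child and a merged result of 24% in one arm and 36% in the other. At least three different situations give it:

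| Dry skin | Nasal | Check on the 36% |
|---|---|---|
| 5% v 20% | 20% v 20% | 1 − 0.80 × 0.80 = 0.36 |
| 5% v 10% | 20% v 28.9% | b = 1 − 0.64/0.90 = 0.289 |
| 5% v 5% | 20% v 32.6% | b = 1 − 0.64/0.95 = 0.326 |

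The merged answer cannot tell a skin-only difference from a nose-only one.

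**Precision of a separate child item at 6 weeks.** For an assumed 5% v 20%, the 95% half-width is 1.96 × √[(0.05 × 0.95 + 0.20 × 0.80)/n] = 1.96 × √(0.2075/n).

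- If the 95 households in section 8.0 are per arm, the 20% loss at 6 weeks leaves n = 95 × 0.8 = 76, and the half-width is 0.102. This reading fits the target of 59 per group, since 95 × 0.8 × 0.9 × 0.9 = 61.6.
- If 95 is the total, n = 38 per arm and the half-width is 0.145.

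**The case against.** **The gap is inferred from silence.** Section 5.0 calls its account an outline, the general question is only an example, research assistants are trained to assess side effects, and the interview form is not in the documents. This stands as a limit: the point concerns the questions as written, and more may be recorded in practice. A reader might infer that the trial certainly fails to record who had what; the documents do not show that. But no probe is described, and section 5.0 lets families answer by post or online on request, with no interviewer present to probe.

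**Family wording suits the burden aim.** Sub Aim 2c concerns families, and time spent is asked for the whole family together. That stands for the aim. It does not reconcile the questions with an outcome defined per participant.

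**The arm comparison survives.** It does, because all parents in both arms get the same prompt. A reader might also infer that asking at family level shrinks the difference between arms. It need not. Under the assumed rates, with skin 5% v 20% and nasal equal at 20%:

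- The merged item differs by 0.36 − 0.24 = 12.0 points for the child.
- For a family of four it differs by (1 − 0.64⁴) − (1 − 0.76⁴) = 0.832 − 0.666 = 16.6 points.
- At 76 per arm, difference over standard error is about 0.120/0.074 = 1.6 for the child and 0.166/0.069 = 2.4 for the family.

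**Serious reactions have another route.** Section 6.0 covers hospitalizations, emergency visits and other problems caused by the protocol. True, but it adds no question on dry skin or nasal symptoms by person.

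**Conclusion.** The point holds for the questions as written, and it is minor. Both side-effect questions give a household answer, the symptom prompt merges skin with nose, and neither matches an outcome defined as a percent of participants at two time points. This is a mismatch between question and outcome as well as missing detail.

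The size is unknown. The illustrations (household yes rates of 42% to 81% against a person rate of 24%) rest on assumed rates and independent members, and clustering would narrow the gap.

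A reader might go further and tie skin complaints to the baths or nasal complaints to the mupirocin. The documents do not support that: component effects are not a trial aim, and the hygiene instructions, given to both arms, include daily washing with soap, so dry skin is not specific to the baths.

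**What to change.** At the 6-week contact, and at the 6-month contact for which the outcome is already listed, ask in both arms, with identical wording:

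- the general side-effect question;
- separate yes/no items for dry or irritated skin, irritation in the nose, and runny nose;
- each of these four once for the index child and once for any other household member.

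Report child items as a percent of index children and other-member items as a percent of households. Present both descriptively by arm with a risk difference and 95% interval. Do not label a symptom as caused by the baths or the mupirocin. If the sponsor means the outcome to cover every enrolled member, these items will not give that percent; it would need a count of affected members.

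Cost: 4 × 2 = 8 yes/no fields at each contact, in place of the two questions now written for 6 weeks. No added visit, call or staff. The downside is some extra seconds per call and several descriptive comparisons instead of one. Under the assumed 5% v 20%, the 6-week report would show a 15-point skin difference in the child, plus or minus about 10 points at 76 per arm or 14.5 at 38.

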In this study, we intend to compare two therapies for MRSA SSTI (abscess surgery and hygiene education compared to abscess surgery and hygiene education followed by decolonization) to determine which is the more effective treatment for MRSA SSTI. We will focus on patient-centered outcomes as described by the families of MRSA infected patients. Such outcomes are likely to include quality of life, side effects, and school and work attendance. The hypothesis is that treatment with decolonization will decrease the rate of SSTI recurrence and improve overall patient-centered outcomes. The rationale is that negative outcomes such as recurrence may be avoided through the use of readily available prevention strategies, however, it is important to determine how burdensome those prevention strategies are for patients and families.

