7.0 Study Withdrawal/Discontinuation

Participants are always free to discontinue any therapy if they find it intolerable at any time. Participants will be encouraged to contact PResNet RA should they decide to do so. At every follow up point, PResNet RAs will attempt to make contact using each phone number up to three times. If they cannot make contact at that point, they will attempt to contact them by email or physical mailing address if those are available. Should those measures fail, the patient will be considered lost to follow-up. When assessments begin, RAs will explain to parents how long the interview should take. If a parent has to interrupt and end an interview, RAs will attempt to schedule a follow-up appointment at which they can continue from where they left off. Should they not be able to re-contact that parent, that patient will be considered lost to follow-up, but that data which has been collected will be used.

Participants are also able to leave the PAB at any time.

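### Weekly hours are asked only of families who report adhering, so the one direct measure of regimen effort for Sub Aim 2c omits families who stopped

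*Combined protocol and SAP*

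**What the plan says.** Sub Aim 2c (section 2.0) is to "Determine the burden and patient preferences regarding the decolonization protocol on families". Section 1.0 gives the reason: "it is important to determine how burdensome those prevention strategies are for patients and families".

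The outcomes list in section 5.0 includes "Estimated weekly time to adhere to intervention by parental report at 6 weeks". The interview instructions later in section 5.0, under the paragraph on time committed to the intervention, set the condition: "If participant report that they adhere to the protocol, the RA will ask parents to estimate the amount of time (in hours) per week". The estimate covers all family members combined and is taken once, at about 6 weeks.

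In the paragraph just before, on side effects, the symptom prompt has no such condition: "All parents will also be asked". Section 7.0 foresees stopping: "Participants are always free to discontinue any therapy if they find it intolerable at any time".

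**The concern.** Time demand is one plausible reason for giving up a regimen of repeated baths and nasal ointment for a whole household. The condition makes the time question depend on not having given up. A family that abandoned the baths in the second week would most naturally report that it did not adhere, and would then not be asked how long the baths took or why it stopped.

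The plan would end with an estimate of hours among families who managed the regimen. A clinician deciding whether to recommend decolonization needs to know what it asks of families to whom it is assigned, including those who could not keep it up. If the two differ, the reported hours would make the regimen look lighter than it is. Information on hours and reasons that is not collected at the 6-week call cannot be reliably recovered later.

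**Working it through.** The plan gives no figure for hours or for the expected adherence rate, so there is nothing to reproduce. The check is a reading of the text, followed by illustrations whose assumptions are marked.

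**1. Does anything else in the plan fill the gap?**

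- Adherence of child and household is asked of everyone reached. It records that a family stopped, but not the hours or the reason.
- Side effects are asked of everyone. They are a different part of burden.
- PedsQL is collected regardless of adherence. It measures the child's general quality of life.
- The free-time item is introduced as an effect of the protocol, but its wording asks about the MRSA diagnosis.
- School and work absence is counted when due to MRSA infection, not when due to the regimen.

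Weekly hours is therefore the only listed item that directly measures regimen effort, and it is the one with the condition.

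**2. Who passes the condition?** Section 5.0 announces a five-point adherence scale, prints three labels, and says that three responses "will be considered adherent to treatment" for analysis; two of those three are not among the printed labels. It does not say which answers open the time question. Families answering in the middle of the scale may or may not be asked. Families who stopped are left out on either natural reading.

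**3. How many families?** Section 8.0 gives an enrolment target of 95 households (read as per group, because the final target is 59 in each) and 20% drop-out by 6 weeks.

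- Reached at 6 weeks: 95 × 0.80 = 76 per group.
- Assumed adherent share 50%: 76 × 0.5 = 38 asked, 38 not asked.
- Assumed adherent share 90%: 76 × 0.9 ≈ 68 asked, about 8 not asked.

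**4. How far could the mean move?** From the description of intervention 2 in section 5.0, soaking takes 2 × 15 min = 0.5 h per person per week. Assume that all members take part, that soaks add up person by person, and that there are equal numbers of two-person (2 × 0.5 = 1 h) and six-person (6 × 0.5 = 3 h) households. The mean over all households is (1 + 3)/2 = 2.0 h.

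With adherence a in small and b in large households, the mean among adherers is (a × 1 + b × 3)/(a + b).

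| a | b | Mean among adherers | Against 2.0 h |
|---|---|---|---|
| 0.8 | 0.8 | (0.8 + 2.4)/1.6 = 2.00 h | no bias |
| 0.8 | 0.6 | (0.8 + 1.8)/1.4 = 1.86 h | about 7% low |
| 0.8 | 0.5 | (0.8 + 1.5)/1.3 = 1.77 h | about 12% low |
| 0.8 | 0.3 | (0.8 + 0.9)/1.1 = 1.55 h | about 23% low |
| 0.6 | 0.8 | (0.6 + 2.4)/1.4 = 2.14 h | about 7% high |

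A second illustration, by simulation, lets the odds of adhering fall by a factor of exp(−0.5) to exp(−1.5) per standard deviation of required time. Mean time among adherers is then below that of all households by 0.24 to 0.53 SD at 50% adherence, 0.14 to 0.33 SD at 70%, and 0.05 to 0.12 SD at 90%. It is zero if adherence and time are unrelated.

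**5. Between arms.** The condition applies in both arms. Any comparison of hours would set adherers in one arm against adherers in the other, that is, groups formed after assignment.

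**The case against.** The outcomes list speaks of the time it takes to adhere, and families who adhered are the ones who can report that. On this view the interview condition simply carries out the outcome definition. This stands as far as it goes: the two parts of section 5.0 do not contradict each other, and time among adherers is a legitimate quantity. But it is not the burden on families to whom decolonization is assigned, and no other item supplies that.

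Families may also stop because of side effects, forgetting or disbelief, so selection need not run with time. This stands too, and makes the direction of bias conditional.

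A reader might infer more than the documents support:

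- That Sub Aim 2c as a whole is answered in a selected group. It is not; side effects, adherence and PedsQL carry no such condition.
- That hours must be understated, or that a finding of low burden is predetermined. The plan gives no adherence rate and no threshold for what counts as burdensome, and the bias is zero if adherence is unrelated to time.
- That a planned randomized test is spoiled. No between-arm test of hours is specified and Sub Aim 2c concerns the decolonization protocol only. Section 4.0 also lets families already using bleach baths be placed in that arm without randomization, so this condition is not the first departure from a randomized comparison.

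**Conclusion.** The point holds for the weekly-hours item. As written, that item estimates time among self-reported adherers, with the cut for adherence left undefined, and nothing is learned about time or reasons from families who stopped.

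If adherence falls as required time rises, the mean is too low: by about 7% to 23% in the household illustration, or 0.05 to 0.53 SD in the selection model. Both rest on assumed adherence rates. The household figures also count soaking time only and assume that it adds up across members.

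Recurrence, repeat surgery and the sample size are not touched. This is a worthwhile, inexpensive improvement to one secondary measure.

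**What to change.** Remove the adherence condition from the time question. At the 6-week contact, ask every family reached, in both arms, how many hours per week the assigned intervention took in the weeks they did it. Ask families who stopped or cut back when they did so and why. Report hours for all families by assigned arm, with adherers as a labelled subgroup, and state which adherence answers define that subgroup. Families who never started have no hours to give; count them separately.

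Deleting the condition alone is not enough. If families who had stopped were asked for weekly hours without reference to the weeks they took part, they could answer zero or close to it, which would pull the mean down again.

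The cost is one or two questions in a call already planned and a change to the branching in the REDCap form. Recall from families who stopped will be noisier, and the change does not recover the 20% expected to be lost by 6 weeks. The adherer estimate remains available.
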